### **6.10.2 Specimen Shipment**

Research staff will transport specimens collected at the University of Maryland Medical Center to the appropriate laboratory on campus. Specimens collected at Mercy Medical Center will be frozen and transported monthly to the laboratory of [name]. Aliquots of urine for La and Rh measurements by HPLC will be shipped to our collaborator [name] at the University of Calgary, Canada, for HPLC. All specimens will be accompanied by a shipping invoice indicating the sample ID and the chain of custody. Specific transport procedures are detailed in the MOP.

## 7 SAFETY REPORTING AND SAFETY MONITORING

Regulatory requirements including the FDA regulations, ICH Guidelines for Good Clinical Practice, and EU Clinical Trials Directive set forth safety monitoring and reporting responsibilities of sponsors and investigators to ensure the safety and protection of human subjects participating in clinical trials.

### 7.1 Responsibilities

Investigators participating in this clinical trial are responsible for and will:

- ∞ evaluate subject safety including assessment of adverse events (AEs) for seriousness, severity, and causality,
- ∞ notify the sponsor of SAEs immediately,
- ∞ provide detailed written reports, including necessary documentation requested by the sponsor or IRB, promptly following immediate initial reports, and
- ∞ inform the IRB of AEs as required by applicable regulatory requirements.

### 7.2 Definitions

#### Adverse Event (AE)

Any untoward medical occurrence clinical investigation subject who has received a study intervention and that does not necessarily have to have a causal relationship with this treatment. An AE can, therefore, be any unfavorable and unintended sign (including an abnormal laboratory finding, for example), symptom, or disease temporally associated with the use of a medicinal product, whether or not considered related to the medicinal product.

#### Serious Adverse Event (SAE)

An SAE is any adverse event that results in any of the following outcomes:

- ∞ Death;
- ∞ Life-threatening (immediate risk of death);
- ∞ Inpatient hospitalization or prolongation of existing hospitalization;
- ∞ Persistent or significant disability or incapacity;
- ∞ Congenital anomaly/birth defect;

- ∞ Important medical events that may not result in death, be life threatening, or require hospitalization may be considered a serious adverse event when, based upon appropriate medical judgment, they may jeopardize the subject and may require medical or surgical intervention to prevent one of the outcomes listed in this definition. Examples of such medical events include allergic bronchospasm requiring intensive treatment in an emergency room or at home, blood dyscrasias or convulsions that do not result in inpatient hospitalization, or the development of drug dependency or drug abuse.

### **Unexpected**

An adverse reaction, the nature or severity of which is not consistent with the applicable product information (e.g., investigator's brochure for an unapproved investigational medicinal product).

### **Expedited Safety Report**

Documentation in appropriate form and format summarizing an SAE that meets expedited safety reporting criteria, submitted within the required reporting time frame of applicable regulatory authorities and/or IRBs/IECs of participating countries.

## **7.3 Safety Reporting Requirements**

### **7.3.1 Reporting Interval**

Document all adverse events (AEs) and SAEs from enrollment through PND21.

All SAEs will be followed until resolution even if this extends beyond the study-reporting period. Resolution of an adverse event is defined as the return to pre-treatment status or stabilization of the condition with the expectation that it will remain chronic.

The investigator will follow all SAEs until resolution (return to pretreatment status or stabilization of the condition with the expectation that it will remain chronic) even if this extends beyond the study-reporting period.

### **7.3.2 Notification of the Sponsor of Serious Adverse Events**

Any AE that meets a protocol-defined serious criterion that are associated with study product(s) must be submitted within 24 hours of site awareness to the sponsor, and IRB.

Other supporting documentation of the event may be requested by the sponsor and should be provided as soon as possible.

### **7.3.3 Regulatory Reporting for Studies Conducted Under Sponsored IND**

Following notification from the investigator, the sponsor will report events that are both serious and unexpected and that are associated with study product(s) to the Food and Drug Administration (FDA) within the required timelines as specified in 21 CFR 312.32: fatal and life-threatening events within 7 calendar days (by phone or fax) and all other SAEs in writing within 15 calendar days. All serious events designed as “not associated” to study product(s) will be reported to the FDA at least annually in a summary format.

## **7.4 Investigator's Assessment of Adverse Events**

The determination of seriousness, severity, and causality will be made by an on-site investigator who is qualified (licensed) to diagnose adverse event information, provide a medical evaluation of adverse events, and classify adverse events based upon medical judgment. This includes but is not limited to physicians, physician assistants, and nurse practitioners.

### **7.4.1 Assessment of Seriousness**

Event seriousness will be determined according to the protocol definition of an SAE (Section 7.2). *Severity will be determined according to neonatal toxicity table (Appendix D) and expanded table of severity for laboratory values (Appendix E).*

### **7.4.2 Assessment of Severity**

Event severity will be assigned according to the definitions below:

- ∞ Mild: events require minimal or no treatment and do not interfere with the study subject's daily activities.
- ∞ Moderate: events result in a low level of inconvenience or concern with the therapeutic measures. Moderate events may cause some interference with functioning.
- ∞ Severe: events interrupt a study subject's usual daily activity and may require systemic drug therapy or other treatment. Severe events are usually incapacitating.
- ∞ Life-threatening

### **7.4.3 Assessment of Association**

The association assessment categories that will be used for this study are:

- ∞ Associated – The event is temporally related to the administration of the study product and no other etiology explains the event.

- ∞ Not Associated – The event is temporally independent of the study product and/or the event appears to be explained by another etiology.

The investigator must provide an assessment of association or relationship of AEs to the study intervention based on:

- ∞ Temporal relationship of the event to the study intervention
- ∞ Whether an alternative etiology has been identified;
- ∞ Biological plausibility;
- ∞ Existing therapy and/or concomitant medications.

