IP more rapidly in the first month of life compared with cow milk-based formula in term (35) and in preterm neonates (36).

[figure not shown]
***NEC and its pathogenesis:*** NEC, a life-threatening, GI emergency characterized by increased IP, affects approximately 7 to 10% of preterm neonates, and typically occurs within 7 to 14 days of birth (37, 38) with mortality as high as 30-50% (39). NEC symptoms mainly involve GI dysfunction, such as abdominal distension and feeding intolerance, but the presentation can be non-specific with few warning signs. Current therapies may be invasive, including surgical interventions that are often ineffective due to the rapid progression of the disease. Prematurity is the greatest risk factor for development of NEC (40, 41), due to physiological immaturity of the GI tract and altered levels of the normal GI microbiota. Several studies suggest that the initiation of an intense systemic and local inflammatory cascade leads to intestinal necrosis (42-47). Antenatal exposure to infection/inflammation may predispose the developing intestinal mucosa to subsequent injury or dysregulated inflammatory responses. Previous studies have linked presence of amniotic fluid infection/elevated cytokines, (48) cord blood cytokines, (49, 50) and umbilical cord inflammation (51) with risk for NEC in preterm neonates. In a rat model of NEC, maternal prenatal exposure to microbial LPS led to increased frequency and severity of intestinal injury (52). Taken together, these observations suggest that intestinal injury may be initiated *in utero* and contributes to increased IP at birth in the preterm neonate. Many of the defense mechanisms present in the mature intestine, such as peristalsis and tight junctions between intestinal epithelial cells (37) are decreased in an immature intestine, and thus bacteria normally confined to the intestinal lumen are able to reach systemic organs and tissues. Bacterial translocation triggers the activation of an exaggerated inflammatory response, which leads to further epithelial damage.

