## 8 CLINICAL MANAGEMENT OF EVENTS

### 8.1 Adverse Event Management

Study interventions will not influence medical care. Morbidities associated with prematurity are protocol-specified potential serious adverse events. These are events that are anticipated to occur in the preterm population even in the absence of study intervention. Morbidities of prematurity will be recorded on CRFs on study day 21 or discharge/transfer whichever comes first.

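### The two-category rule in 7.4.3 makes a serious gastrointestinal event after the dose, such as NEC, hard to class as Associated, so it may miss the reports that depend on that label

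*Combined protocol and SAP*

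**What the plan says.** Section 7.4.3 gives two association categories. An event is Associated if "The event is temporally related to the administration of the study product and no other etiology explains the event". It is Not Associated if it is unconnected in time with the product and/or "the event appears to be explained by another etiology". Below the definitions the section adds "The investigator must provide an assessment of association or relationship of AEs to the study intervention based on" four factors: timing, whether an alternative cause has been identified, biological plausibility, and existing or concomitant therapy.

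Two reporting routes use the label. Section 7.3.2 covers serious events "that are associated with study product(s) must be submitted within 24 hours of site awareness to the sponsor, and IRB". Section 7.3.3 gives 7- or 15-day FDA reports to events that are serious, unexpected and associated, and adds: "All serious events designed as “not associated” to study product(s) will be reported to the FDA at least annually in a summary format".

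On background risk, section 8.1 says of morbidities of prematurity: "These are events that are anticipated to occur in the preterm population even in the absence of study intervention". Section 2.1 states "Prematurity is the greatest risk factor for development of NEC", and that NEC "affects approximately 7 to 10% of preterm neonates, and typically occurs within 7 to 14 days of birth". Section 6.9 gives the sugar solution once, at 7 to 10 days of age.

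**The concern.** An apparent alternative cause is enough for Not Associated, whatever the timing. In infants of 24 to 32 weeks such a cause is often at hand, and for NEC the protocol itself supplies one. An investigator who applies the definitions literally to NEC beginning soon after the dose will find it hard to choose Associated, even if a contribution from the product seems plausible.

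What is at stake is case-level safety reporting. The test is given under an IND, and section 2.2 notes that few infants below 30 weeks were included in earlier permeability studies. A final statement that no serious event was associated with the product could then owe something to the wording of the definition as well as to the data.

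**Working it through.** The point concerns definitions and reporting routes, so there is no planned figure to reproduce. The check is to apply the definitions case by case and follow the label.

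**Step 1. Apply 7.4.3 to each combination.**

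| Temporal link to dose | Another etiology appears to explain the event | Meets Associated? | Meets Not Associated? |
|---|---|---|---|
| Yes | No | Yes | No |
| Yes | Yes | No | Yes |
| No | Yes | No | Yes |
| No | No | No | Yes |

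The second row is the problem. Because the two limbs of Not Associated are joined by and/or, the temporal link cannot change the result. Biological plausibility is listed as a factor but appears in neither definition, so a literal reading gives it no role in that row.

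**Step 2. Does the second row arise in this study?** NEC onset is put at days 7 to 14 (section 2.1) and the dose at days 7 to 10 (section 6.9). The dosing window lies wholly inside the onset range, so background NEC soon after a dose is to be expected.

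**Step 3. Follow the label for a serious event.**

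| Route | Depends on the association label? |
|---|---|
| 7.3.2, 24-hour notice to sponsor and IRB | Yes |
| 7.3.3, 7/15-day FDA report | Yes, and the event must also be unexpected |
| 7.3.3, annual FDA summary | Receives the Not Associated events |
| 7.1, immediate notice to sponsor | No |
| Appendix C, quality check that SAEs went to sponsor/IRB | No |
| 7.6, interruption on counts of deaths and confirmed NEC above Stage 2 | No |

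Sections 7.1 and 7.3.2 and Appendix C do not agree on which serious events must be reported to the sponsor and IRB. No route other than 7.3.3 leads to an expedited FDA report.

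**Step 4. Context on the 7.6 count.** This is the route that counts NEC whatever its cause. With n infants a year and NEC risk p, the chance of at least 7 cases from background alone is 1 − Σ(k = 0 to 6) C(n,k) pᵏ(1 − p)ⁿ⁻ᵏ. With p = 0.07 to 0.10:

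- n = 50 (the yearly number implied by the 5 to 8 deaths in 7.6, since 50 × 0.10 = 5.0 and 50 × 0.15 = 7.5): 0.06 to 0.23
- n = 78 (157 further infants over 24 months): 0.30 to 0.67
- n = 100 (200 over 24 months): 0.56 to 0.88

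If the rule means more than 7, the ranges are 0.02 to 0.12, 0.18 to 0.53 and 0.40 to 0.79. The accrual rates are assumptions. The 7 to 10% covers all NEC, so the chances for NEC above Stage 2 are lower. At the two higher accrual rates the count may often be reached without any product effect. It prompts aggregate review and takes no account of time from dose.

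**The case against.** The strongest reply is that 7.4.3 asks for judgement. It turns on whether another etiology explains the event, or appears to, and a merely possible cause need not meet that test. Section 2.1 calls prematurity a risk factor, which is not the same as the explanation of a given case. Section 8.1 neither names NEC nor assigns anything to Not Associated; it treats these morbidities as potential serious adverse events. The investigator must also weigh four factors. This stands against any claim that the label is automatic. It does not remove the difficulty, because once an alternative does appear to explain the event, the definitions leave timing and plausibility nothing to decide.

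Second, serious events have routes that ignore the label: section 7.1, Appendix C and the counts in 7.6. This stands as a partial offset. The first two conflict with 7.3.2, however, and 7.6 works in aggregate. Its later sentence on serious, unexpected and related events again depends on the label, and section 7.5 makes the sponsor-investigator the safety monitor.

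Third, sections 2.1 and 2.4.1 report the sugar test as safe in newborns, with no risks reported in the literature. That bears on how likely a true association is. It does not bear on whether the definition could record one.

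A reader might infer that all gastrointestinal events after the dose default to Not Associated and bypass expedited reporting. The documents do not support this. Besides the two replies above, non-serious events never enter the 24-hour or 7/15-day routes, and an FDA expedited report also requires the event to be unexpected.

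**Conclusion.** The point holds as a weakness in a stated rule, worth correcting because correction is cheap. Section 7.4.3 can place a serious post-dose event in Not Associated on an apparent alternative cause alone. For NEC in this population such a cause is usually at hand. Such an event may miss the 24-hour notice in 7.3.2 and, if unexpected, reach the FDA only in the annual summary.

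Its size cannot be estimated from the documents. A reader might take the background totals for the 157 further infants as the size: 157 × 0.07 to 0.10 = 11 to 16 NEC cases, and 157 × 0.10 to 0.15 = 16 to 24 deaths. They do not measure misclassification. They are the events expected with no product effect, for which Not Associated would be right. Some would precede the dose or occur in infants never dosed. The mortality figure is for the whole hospital stay, whereas section 7.3.1 documents events only through day 21.

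The conclusion assumes that investigators apply the two definitions as worded and follow 7.3.2 where it differs from 7.1 and Appendix C.

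**What to change.** - In 7.4.3, define Associated as a reasonable possibility that the product contributed, judged on the four factors already listed there. Define Not Associated as no plausible temporal link, or a specific identified alternative cause that makes a contribution unlikely.
- State that being an anticipated morbidity of prematurity does not by itself settle the assessment. A blanket rule that prematurity can never be a sufficient cause is not proposed: it could push background NEC into Associated and blur a real signal.
- Record time from dose to onset for serious events, if the adverse event forms (IP10 and IP11) do not already capture it. The forms are not in the documents.
- Reconcile 7.1, 7.3.2 and Appendix C on which serious events go to the sponsor and IRB, and when.

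The cost is a wording change and at most one added field. The downside is somewhat more events labelled Associated and more expedited reports.

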#### **7.4.4 Assessment of Reactogenicity (*if applicable*)**

*Not applicable.*

### **7.5 Safety Monitoring**

Safety Monitoring: For the continuation of this observational study, the sponsor-investigator will be the Data Safety Monitor to 1) periodically review and evaluate the accumulated study data for subject safety, study conduct and progress, and, when appropriate, efficacy, validity, and integrity and 2) make decisions concerning the continuation, modification, or termination of the study.

#### **7.5.1 Interruption or Discontinuation of Study Enrollment and Study Product Administration for all Subjects in the Study**

Not Applicable

### **7.6 Halting Criteria/Rules**

#### **7.6.1 Stopping Rules for Individual Subjects**

A pre-dose checklist for evidence of feeding intolerance will be completed prior to La/Rh administration. The Lactulose/Rhamnose administration will be re-scheduled within the study window if the clinically indicated gastric residual is obtained and measures >50% of the previous nutritive feeding volume, and/or contains bile or gross blood, or is hemoccult-positive. If these GI signs are present throughout the study window, the La/Rh test will not be administered. Other conditions that would result in delay or discontinuation of the La/Rh test include hypotension requiring pharmacologic support, clinical or radiographic signs of intestinal ileus or NEC. The subject will continued to be followed until postnatal day 21±2 d or discharge/transfer which ever occurs first.

**Plans for Study Interruption Based on Safety Monitoring:**

Since the expected in-hospital mortality rate for infants 24-32 weeks gestation is 10-15% at the UMMC NICU, 5-8 deaths may occur in our study population per year. If more than 10 deaths or 7 confirmed cases of NEC >Stage 2 occur within one year or more than 4 deaths or 3 confirmed NEC cases >Stage 2 in consecutively recruited subjects occur within 30 d of enrollment, the study will be interrupted until reviewed by the safety monitor. The study may also be halted if the number of SAEs overall, the number of occurrences of a particular type of SAE, severe AEs/reactions, or increased frequency of events warrant further investigation. The safety review may require temporary suspension of enrollment or all study interventions. The safety review may determine whether the study should continue per protocol, proceed with caution, be further investigated, be discontinued, or be modified and then proceed. Subsequent review of serious, unexpected, and related AEs by the medical monitor, IRB, the sponsor(s), or relevant local regulatory authorities may also result in suspension of further trial interventions at a site. The study sponsor(s) retain the authority to suspend additional enrollment and study interventions for the entire study, as applicable.

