We propose in this study to recruit additional 157 preterm subjects and to combine with our existing 43 preterm subjects to form a statistically powered cohort at 200 (justified in study size analysis in research design), to address our hypothesis that the two naturally occurring beneficial bacteria *Clostridiales* and *Bifidobacterium* are rapidly gaining prosperity during normal intestine development in association with improved barrier function measured by La/Rh ratio. Overall, this continuation of the initial study builds on the previous findings that identified commensal bacteria *Clostridiales* and *Bifidobacterium* species as a strong indicator to the lowered IP and rapid maturation of intestinal barrier, to substantiate measurement of these probiotic strains combined with associated neonatal factors to form an accurate, rapid detection of intestinal permeability abnormality.

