### 4.2 Exclusion Criteria

Exclusion criteria will include:

- 1) Non-viability or planned withdrawal of life support;
- 2) Triplet or higher order multiple;
- 3) Severe asphyxia (Apgar <3 at 5 min and cord pH <7.0);
- 4) Lethal chromosome abnormalities;
- 5) Cyanotic congenital heart disease;
- 6) Intestinal atresia or perforation;
- 7) Abdominal wall defects;
- 8) Significant GI dysfunction (e.g. heme-positive stools, abdominal distension (girth >2 cm baseline), or bilious emesis/aspirates.
- 9) *Infants with galactosemia or other forms of galactose intolerance*

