### **4.5.2 Handling of Withdrawal**

Subjects who discontinue due to being withdrawn or lost to death will be replaced. Data and specimens will be de-identified and remain as part of the study.

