## 10 STATISTICAL CONSIDERATIONS

### 10.5 Sample Size Considerations

Sample size for primary objective: The sample size for the first aim (50 subjects) will provide good precision in the estimate of the distribution of levels of intestinal permeability at each time point. The quantiles will be accurate +/- 10 percentage points (based on a 95% confidence interval). Based on the sites' combined annual admission numbers and survival rates, we expect 120 infants to be eligible in the 6 month planned enrollment period in the first year. The combined NICU population is approximately 59% male with an ethnic distribution of 65% African-American, 33% Caucasian and 2% other.

Sample size for microbiome analysis: The sample size of 200 was calculated to obtain high precision in correlations between features of the stool microbiota and intestinal permeability (IP). Since 83% subjects in the first cohort had high IP ( $La/Rh \geq 0.05$ ) at study day 8, a sample size of 166-236 provides marginal error of 0.05 (maximum sampling error of 5%) and alpha of 0.05 (95% confidence level) to detect correlations between features of the microbiota and changes in IP and to achieve an expected sensitivity of 0.8-0.9 and expected specificity at 0.9-0.95.

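### Section 7.6: the expected 5-8 deaths a year fits about 50-53 infants a year, not 157 more infants in 24 months, so the stated basis of the more-than-10-deaths trigger needs restating

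*Combined protocol and SAP*

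**What the plan says.** The plan for study interruption in section 7.6 states that, since the in-hospital "mortality rate for infants 24-32 weeks gestation is 10-15% at the UMMC NICU, 5-8 deaths may occur in our study population per year". The rule follows directly: "If more than 10 deaths or 7 confirmed cases of NEC >Stage 2 occur within one year", the study is interrupted until the safety monitor has reviewed it. A second rule covers deaths and NEC cases in consecutively recruited subjects within 30 days of enrolment, and there is a discretionary halt based on the number or type of serious events.

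The figures that bear on annual enrolment are elsewhere:

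- Section 2.3: "We propose in this study to recruit additional 157 preterm subjects", to be combined with the existing 43 for a total of 200.
- Protocol Summary: one site, a study duration of 24 months, and 28 days of participation per infant.
- Section 4.5.2: "Subjects who discontinue due to being withdrawn or lost to death will be replaced".
- Sample Size Considerations (section 10): a first aim of 50 subjects and a "6 month planned enrollment period in the first year".

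The figures that bear on which deaths count are these:

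- Section 7.3.1: "Document all adverse events (AEs) and SAEs from enrollment through PND21", with serious events followed to resolution.
- Section 4.2: several high-mortality groups are excluded, beginning with "Non-viability or planned withdrawal of life support".

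No annual accrual is given for the enlarged study. Section 7.6 does not say over what period after enrolment a death counts towards the annual trigger.

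**The concern.** The 5-8 figure is the only stated expectation behind a mandatory interruption rule. Set against it, more than 10 deaths in a year looks clearly abnormal. If the figure belongs to a smaller annual intake than the one now planned, that comparison is no longer sound. The monitor could be called to review a year with no excess. If mortality in the enrolled infants is well below the quoted rate, a real excess could instead pass below the threshold. In both cases the person reading the count lacks a benchmark that matches the study being run.

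**Working it through.** **Inputs.** Mortality 10-15%, expected deaths 5-8 a year and a trigger of more than 10 deaths in a year (section 7.6); 157 infants still to recruit (section 2.3); duration 24 months (Protocol Summary); first aim of 50 subjects (section 10).

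**Step 1: reproduce the plan's figure.** Expected deaths = infants per year × mortality. Inverting, 5/0.10 = 50 and 8/0.15 = 53.3 infants a year. Forward, 50 × 0.10 = 5.0 and 50 × 0.15 = 7.5, which rounds to 8. The stated 5-8 is correct for about 50 infants a year, the size of the first aim.

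**Step 2: apply the current plan.** With even recruitment over 24 months (an assumption), 157/2 = 78.5 infants a year. Then 78.5 × 0.10 = 7.9 and 78.5 × 0.15 = 11.8 deaths a year. The expected count reaches 10 at a mortality of 10/78.5 = 12.7%.

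**Step 3: chance of crossing the trigger with no excess.** P(X ≥ 11) for X binomial(n, p), with n the infants enrolled in the year:

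| Recruitment of the 157 | Infants a year | Expected deaths at 10-15% | n used | P(>10) at 10% | P(>10) at 15% |
|---|---|---|---|---|---|
| Implied by 5-8 | 50-53.3 | 5-8 | 50 / 53 | 0.9% / 1.5% | 12% / 16% |
| 24 months | 78.5 | 7.9-11.8 | 79 | 16% | 65% |
| 30 months | 62.8 | 6.3-9.4 | 63 | 5% | 34% |
| 36 months | 52.3 | 5.2-7.9 | 52 | 1% | 15% |

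At 12.5% mortality and n = 79 the chance is 40%.

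**Step 4: what would make 5-8 right.**

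- By time: 157/53.3 × 12 = 35.3 months and 157/50 × 12 = 37.7 months, so recruitment of about 35-38 months.
- By rate at 78.5 a year: 5/78.5 = 6.4% and 8/78.5 = 10.2% mortality per enrolled infant over the counted window.

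**Step 5: sensitivity to lower mortality.** At n = 79, P(>10) is 5% at an assumed mortality of 8%, 1.2% at 6.4% and 0.2% at an assumed 5%.

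Replacing infants who die (section 4.5.2) would raise annual enrolment above 78.5. By how much depends on how many deaths occur before the infant completes the study, which the documents do not give.

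**The case against.** The strongest reply is that the 79 a year is not the plan's number. The 24 months is labelled study duration and is not tied to the 157 infants. It may itself be the stale figure: the revision history runs from October 2013 to August 2019, so 24 months cannot cover the whole study including the first 43 infants, and no listed revision changes the duration. If recruitment takes about three years, 5-8 is right and the correction belongs in the Protocol Summary. This stands. It means the documents cannot say which figure is wrong, but the disagreement between them remains.

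A second reply is that 10-15% is a whole-unit, in-hospital rate. Study infants have survived to consent, exclude several high-mortality conditions, and have events documented only to postnatal day 21. Mortality over the counted window is therefore probably lower, and at 5-8% the trigger would rarely be crossed by chance. This also stands, and it bars two stronger readings. A reader might infer that the trigger sits inside the range of deaths the study should really expect, or that the duration, the mortality rate and the 5-8 figure are strictly incompatible. The documents support neither. The first needs both the inferred intake and the undiscounted unit rate. The second ignores that 6.4-10.2% per enrolled infant would reconcile the three. But section 7.6 itself applies 10-15% to the study population and mentions no discount.

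Third, the consequence is modest. The rule pauses the study for review, the review may let it continue, and the intervention is a single planned sugar dose. This stands too and limits the weight of the point.

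**Conclusion.** The concern holds as a mismatch between figures in the current text. It is not an arithmetic slip: 5-8 follows from 10-15% at 50-53 infants a year. It does not follow from 157 infants in 24 months, where the plan's own rate gives about 8-12 deaths a year and a 16-65% chance of crossing the trigger with no excess, against about 1-16% at 50-53 a year.

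These figures rest on even recruitment over 24 months and on the unit rate applying unchanged to enrolled infants. The first is inferred and the second is probably too high. Whether the threshold is too sensitive or too insensitive therefore cannot be determined from the documents. What can be said is that the stated basis of a mandatory interruption rule does not agree with the plan's own rate, sample and duration. It should be corrected. The effect is limited because the 30-day consecutive-subject rule, the NEC rules and the discretionary halt do not depend on 5-8, and no endpoint or analysis is affected.

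**What to change.** In section 7.6:

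1. State the currently planned annual enrolment. If 24 months is the outdated figure, correct the study duration in the Protocol Summary.
2. State the unit's historical mortality among infants meeting sections 4.1 and 4.2 over a defined counting window: enrolment to postnatal day 21, or enrolment to discharge if all known in-hospital deaths are to count.
3. Restate the expected annual deaths from these two inputs, and say that the annual trigger counts deaths over the same window.
4. Have the safety monitor confirm or reset the threshold of more than 10 against the restated figure.

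The cost is a small chart count from records the unit should hold and a few sentences of text. The downside is that the threshold may change, so safety reviews could become more or less frequent. Design, sample size and analyses are untouched.
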